6.2 Primary outcome tool

HAP is an acute lower respiratory tract infection that is acquired after at least 48 hours of admission to hospital and is not incubating at the time of admission (BMJ best practice; Hospital acquired pneumonia (non covid-19) 2022). It is more common in patients that have undergone major surgery, those admitted to critical care, and those with a prolonged hospital admission (BMJ no 6 best practice). Developing a HAP is associated with an increase in morbidity and mortality as patients with these risk factors are also likely to have one or a combination of multiple co-morbidities, critical illness and frailty. Using a standardised outcome measure to assess the primary outcome reduces the risk of bias and increases reliability and reproducibility. The primary outcome in this study was hospital-acquired pneumonia as defined by the British Medical Journal (BMJ), best practice guidelines on hospital-acquired pneumonia (non-covid-19). The criteria are the following;

A new and/or persistent shadowing (consolidation) on chest x-ray, which is otherwise unexplained, plus at least two of the following confirms the diagnosis:

- Fever $>38^{\circ}\text{C}$ ($>100^{\circ}\text{F}$)
- Leukocytosis ($\text{WBC} >10 \times 10^9/\text{L}$) or leucopenia ($\text{WBC} <4 \times 10^9/\text{L}$)
- Purulent sputum
- Decline in oxygenation

The primary investigator will identify eligible patients from a database collected as part of routine clinical care, trust service evaluation and audit. Electronic and paper records from eligible patients will be screened and data relevant to the study extracted and recorded. This data will then be analysed.

7 Subject selection

Participants will be identified by screening consecutive sets of case notes and electronic records for the years of 2014 (those before tracheostomy insertion was routine, therefore those who did not have a tracheostomy inserted) and 2017 (tracheostomy insertion was routine). Eligibility criteria includes all patients who underwent oromaxillofacial surgery with tracheostomy and free flap reconstruction. Only those with missing or unavailable data will be excluded. The PI is an employee of Guy's and St Thomas' NHS foundation trust (GSTT) and will be undertaking all aspects of data collection and recording. As employees of GSTT the CI and PI have undertaken all relevant information governance mandatory training permitting access to required data. The study will take place at a single site – Guy's & St Thomas' NHS Foundation Trust.

7.1 Subject inclusion criteria

- Patients who underwent maxillofacial resection with free flap reconstruction and tracheostomy from 1st January 2018 to 31st December 2018.
- Patients who underwent maxillofacial resection with free flap reconstruction and with endotracheal intubation from 1st January 2014 to 31st December 2014
- Patients over the age of 18

7.2 Subject exclusion criteria

- Patients who did not undergo maxillofacial resection with free flap reconstruction and tracheostomy from 1st January 2018 to 31st December 2018 – not relevant and will not answer the study question
- Patients who did not undergo maxillofacial resection with free flap reconstruction and with endotracheal intubation from 1st January 2014 to 31st December 2014 - not relevant and will not answer the study question
- Patients under the age of 18

8 Study procedures

8.1 Subject recruitment

Subjects will not be recruited or consented. The study is a retrospective observational cohort study, reviewing retrospective data collected as part of routine clinical care.

8.2 Screening Procedures

The primary investigator will identify eligible patients from a database collected as part of routine clinical care, trust service evaluation and audit.

8.3 End of Study Definition

Full data collection and analyses.

9 Assessment of Safety

The study is an observational cohort study, involving analysis of retrospective patient data collected as part of routine clinical care. There are no interventions or contact with patients. The primary investigator is an employee of GSTT, and is directly involved in the delivery of clinical care to this patient group in their normal clinical role.

9.1 Ethics Reporting

The study is an observational cohort study, involving analysis of retrospective patient data collected as part of routine clinical care. There are no interventions or contact with patients.

10 Data

10.1 Data to be collected

The PI will identify eligible patients from a database collected as part of routine clinical care for trust service evaluation and audit. Electronic and paper records of eligible patients will be screened and data appropriate to the study extracted. Descriptive demographic data including age, gender, cancer site, stage, surgery type, neck dissection, flap site, and factors known to increase risk of HAP; smoking history, respiratory history, tumour size, hospital length of stay, and mortality will be recorded. The primary outcome tool will be retrospectively applied to case notes and electronic records of included patients, by a single therapist (the PI) between day 1 and 7 post operatively. It is anticipated data collection will take around 2 months.

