4.5 Endotracheal and Nasopharyngeal intubation

Despite temporary tracheostomy insertion continuing to be the preferred choice for airway security, there is some evidence that the current approach might need to adapt; patient experience data has shown that given the choice, patients would avoid tracheostomy formation if possible (Nakarada-

Kordic, Patterson, Wrapson, and Reay (2018)). Furthermore there are studies demonstrating that patients who undergo these procedures can be safely managed with overnight intubation. M. J. Coyle et al. (2013), and Singh et al. (2016) both demonstrated that overnight ETT intubation was associated with a lower rate of HAP (10% vs 38% and 6% Vs 12% respectively), and shorter hospital length of stay (12.9 Vs 18.0 days and 20.4 Vs 27.2 days P=0.03 respectively). Despite these data demonstrating more favourable outcomes when compared with tracheostomy, standardised criteria to assess complication outcomes were not used increasing the risk of detection bias. Statistical integrity is also questionable due to absent power calculations or small sample sizes. As a result the evidence justifying intubation remains equivocal. However, anecdotally, the evidence supports the notion that not only will patients avoid the risks and morbidity associated with tracheostomy insertion, they will be able to speak cough and clear secretions independently sooner (Coyle 2012) which will positively impact their overall post-operative recovery and experience.

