10.2 Primary outcome tool

HAP is an acute lower respiratory tract infection that is acquired after at least 48 hours of admission to hospital and is not incubating at the time of admission (BMJ best practice). It is more common in patients that have undergone major surgery, those admitted to critical care, and those with a prolonged hospital admission (BMJ no 6 best practice). Developing a HAP is associated with an increase in morbidity and mortality as patients with these risk factors are also likely to have one or a combination of multiple co-morbidities, critical illness and frailty. Using a standardised outcome measure to assess the primary outcome reduces the risk of bias and increases reliability and reproducibility. The primary outcome in this study was hospital-acquired pneumonia as defined by the British Medical Journal (BMJ), best practice guidelines on hospital-acquired pneumonia (non-covid-19), the criteria is the following;

A new and/or persistent shadowing (consolidation) on chest x-ray, which is otherwise unexplained, plus at least two of the following confirms the diagnosis:

- Fever $>38^{\circ}\text{C}$ ($>100^{\circ}\text{F}$)
- Leukocytosis ($\text{WBC} >10 \times 10^9/\text{L}$) or leucopenia ($\text{WBC} <4 \times 10^9/\text{L}$)
- Purulent sputum
- Decline in oxygenation

Data collected will be continuous, nominal, ordinal and discrete.

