Patient's hospital numbers will not be held in the same database as clinical data. It will be stored in a separate database and linked through a unique study number. On initial identification it will be stored in a separate password protected database that will be saved on a secure trust laptop, stored in a locked cabinet in a room that can only be accessed with trust swipe ID access.

The data (stored on password protected computers that are stored in a secure office of the PI at Guy's Hospital Site) generated by the study will be analysed in commercially available software (SPSS) by the PI.

The data will not include any participant identifiable data. Anonymized participant characteristic and study data for this study will be stored securely in Microsoft Excel files – it is a small non-interventional observational study and while we do not envisage the characteristic data changing, if it does then separate files will be created to create an audit trail.

The data will be analysed on the Guy's Hospital site, on a GSTT laptop, by the PI only. All participant-identifiable data will have already been removed from the laptop and transferred to an encrypted external storage device (an encrypted USB device provided by the GSTT IT department kept in a locked filing cabinet in locked, secured offices in an area that can only be entered with a security swipe-card at Guy's Hospital. The encrypted external storage device will be backed-up on a secure networked digital datastore that is accessible only to the PI on PCs that are password protected at login kept in locked, secured offices in an area that can only be entered with a security swipe-card at Guy's hospital. Any GSTT laptop will not therefore have participant-identifiable data kept on its hard drive.

Excel spreadsheets will be used, data stored within excel spreadsheets will be periodically saved as a PDF (to lock the data) and saved in a password protected folder with the Excel database. The PDF will be printed off and validated by the PI. A hard copy will be retained securely should the Excel file become corrupt as a back-up.

Data Protection:

Data will be processed according to trust information governance processes and the PI is compliant with all information governance mandatory training and good clinical practice principles

No data will be obtained that is not required for the current study and its stated end points

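### HAP status is judged by one investigator with no masking described and no component data named; recording the components and computing HAP by a pre-set rule would narrow, not remove, the detection bias

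*Combined protocol and SAP*

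**What the plan says.** Under 10.1 the HAP tool is "retrospectively applied to case notes and electronic records of included patients, by a single therapist (the PI"), covering postoperative days 1 to 7. Section 7 says the same person "will be undertaking all aspects of data collection and recording". Sections 8.2 and 10.1 have that person identify eligible patients, and the criteria in 7.1 are defined by year and airway method. Section 10.3 has the analysis done by the PI alone. Section 9 adds that the investigator "is directly involved in the delivery of clinical care to this patient group in their normal clinical role".

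The definition in 6.2 and 10.2 requires "shadowing (consolidation) on chest x-ray, which is otherwise unexplained", plus at least two of four items: fever, abnormal white cell count, purulent sputum and "Decline in oxygenation". Fever and white cell count have numeric cut-offs. Oxygenation has none.

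The list of data to record in 10.1 covers demographics, tumour and surgical details, risk factors, length of stay and mortality. It does not name the x-ray finding, temperature, white cell count, sputum or oxygen values. Section 10.3 plans coded spreadsheets. Of the hospital number it says: "It will be stored in a separate database and linked through a unique study number".

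Section 4.5 faults earlier studies because "standardised criteria to assess complication outcomes were not used increasing the risk of detection bias".

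**The concern.** Someone who selects records by year and airway knows the cohort when deciding whether HAP was present. The protocol never says the assessor is unmasked. That follows from the combination of roles and from the absence of any masking, second reader or agreement check.

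Section 4.7 describes HAP as a perceived risk of tracheostomy, so there is a documented expectation that could colour borderline calls. If doubtful 2018 cases are called positive more readily than doubtful 2014 cases, the difference goes straight into the primary comparison. Neither the chi-square test nor the logistic regression in 11.2 can separate it from an effect of the airway method. If the components are not kept, nobody can later check or re-derive the classification.

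**Working it through.** **The plan's own figure.** Inputs from 11.1: odds ratio 2.33, 30% HAP in the 2014 cohort, 41% of patients in the 2018 cohort, 80% power, two-sided 5%.

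- Odds in 2018 = 2.33 × 0.30/0.70 = 0.9986, so the rate is 0.9986/1.9986 = 49.96%.
- N = (1.960√V0 + 0.842√V1)² / (ln 2.33)², the Wald test for a binary predictor with variance correction.
- Overall rate = 0.59 × 0.30 + 0.41 × 0.4996 = 0.3819.
- V0 = 1/(0.3819 × 0.6181 × 0.41 × 0.59) = 17.51.
- V1 = 1/(0.59 × 0.30 × 0.70) + 1/(0.41 × 0.4996 × 0.5004) = 17.83.
- N = 193.2, against the stated 193.

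The sample size reproduces, and this point does not change it. Cohort sizes are 0.41 × 193 = 79 for 2018 and 114 for 2014. Section 11.1 labels the 2018 cohort as intubated and section 7 gives 2017 as the tracheostomy year. I follow 7.1 and take the 79 as tracheostomy patients; these labels need reconciling separately.

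**Illustration of differential misclassification.** Sensitivity and specificity are assumptions; the documents give none. The direction, lower specificity in the tracheostomy cohort, is also assumed.

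Observed rate = true rate × sensitivity + (1 − true rate) × (1 − specificity).

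The true rate is 30% in both cohorts, sensitivity is 90% in both, and specificity is 95% for intubation. The observed intubation rate is then 0.30 × 0.90 + 0.70 × 0.05 = 30.5%. The false-positive rate comes from exact enumeration of both binomials, using the uncorrected chi-square test at 5% with 114 versus 79.

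| Specificity, tracheostomy | Observed rate, tracheostomy | Apparent OR | False-positive rate |
|---|---|---|---|
| 95% (no gap) | 30.5% | 1.00 | 5.0% |
| 93% (2 points) | 0.27 + 0.70 × 0.07 = 31.9% | 1.07 | 5.6% |
| 90% (5 points) | 0.27 + 0.70 × 0.10 = 34.0% | 1.17 | 8.3% |
| 85% (10 points) | 0.27 + 0.70 × 0.15 = 37.5% | 1.37 | 17.8% |

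Equal error in both cohorts leaves the test at its nominal level, so the inflation comes only from the difference between cohorts. It is larger if HAP is rarer than planned. At a true rate of 10% in both, the 5- and 10-point gaps give observed rates of 13.5% versus 18.0% and 22.5%, odds ratios of 1.41 and 1.86, and false-positive rates of 13.6% and 36.8%.

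**What the fix acts on.** Computing HAP by formula removes discretion in combining items. Pre-set rules narrow it for oxygenation and sputum. Neither affects which entries an unmasked extractor finds and copies, nor differences between 2014 and 2018 in how often tests were done or charted. The documents hold nothing from which to split total error into these parts, so no before-and-after figure can be given.

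**The case against.** The strongest reply is that the protocol has already dealt with the fault it finds in earlier work. Those studies lacked standardised criteria. This one has a written counting rule with numeric limits for fever and white cell count, and it gives bias reduction as the reason for using it. That stands in part: the remaining discretion is narrower than in the studies criticised. It is still not closed, because three elements remain open to interpretation.

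A second reply is that the fix works mainly on the combining step, which is the least open to bias. Coding a sputum note and deciding whether shadowing is unexplained remain judgements. X-ray wording may reveal the airway, and a person who has just extracted every record is only weakly masked by hidden columns. All of that stands, and it limits the claim to a reduction. Re-classifying a sample would not help either, since a consistent bias would show good agreement.

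Third, the larger inflation figures need a 10-point specificity gap, and the largest also needs a 10% true rate, whereas 11.1 assumes 30% for 2014. A 2-point gap is almost harmless. This also stands.

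Two stronger readings are tempting but unsupported. A reader might infer that the investigator treated the patients being classified. Section 9 says only that the investigator is "directly involved in the delivery of clinical care to this patient group in their normal clinical role", in the present tense, and does not place that person in the care of any 2014 or 2018 patient. A reader might also infer that a bare yes or no will be recorded in a single step. The protocol does not say so; it is silent on whether the components are kept.

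**Conclusion.** The point holds as a cheap improvement that should be made. The primary outcome rests on one person who knows the cohort, with no masking described, no component data named and no threshold for oxygenation. The standardised definition limits detection bias without removing it.

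Under the assumed error rates, at the planned size and a 30% true rate, the false-positive rate runs from about 6% for a 2-point specificity gap to about 18% for a 10-point gap. These figures show sensitivity to group-dependent judgement. They are not evidence that such judgement will occur, nor a measure of what the fix would gain. A reader might infer that any excess of HAP after tracheostomy would be an artefact, or that a computed rule would make the outcome free of bias. The documents support neither conclusion.

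**What to change.** In 10.1 and 10.2:

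1. Name the dated components as data to be recorded in the coded spreadsheet already planned in 10.3: chest x-ray report wording, temperature, white cell count, sputum entry and charted oxygen values.
2. Before extraction, set one numeric oxygenation rule and one coding rule for sputum wording, both applied identically to the two years. State whether the items must coincide in time, and how the day 1 to 7 window relates to the 48-hour element of the definition, since a formula needs both.
3. Compute HAP by formula from those cells.
4. Where practical, code the x-ray and sputum text on shuffled rows with year and airway hidden.
5. State as a limitation that this reduces but does not remove detection bias, because extraction stays unmasked and differences between years in testing and charting remain.

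The cost is a few lines of text, more spreadsheet columns and extra extraction time for the investigator within the planned period of about 2 months. That time could be appreciable for daily values from partly paper notes on 193 patients. No extra staff are needed and the sample size does not change.

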10.2 Primary outcome tool

HAP is an acute lower respiratory tract infection that is acquired after at least 48 hours of admission to hospital and is not incubating at the time of admission (BMJ best practice). It is more common in patients that have undergone major surgery, those admitted to critical care, and those with a prolonged hospital admission (BMJ no 6 best practice). Developing a HAP is associated with an increase in morbidity and mortality as patients with these risk factors are also likely to have one or a combination of multiple co-morbidities, critical illness and frailty. Using a standardised outcome measure to assess the primary outcome reduces the risk of bias and increases reliability and reproducibility. The primary outcome in this study was hospital-acquired pneumonia as defined by the British Medical Journal (BMJ), best practice guidelines on hospital-acquired pneumonia (non-covid-19), the criteria is the following;

A new and/or persistent shadowing (consolidation) on chest x-ray, which is otherwise unexplained, plus at least two of the following confirms the diagnosis:

- Fever $>38^{\circ}\text{C}$ ($>100^{\circ}\text{F}$)
- Leukocytosis ($\text{WBC} >10 \times 10^9/\text{L}$) or leucopenia ($\text{WBC} <4 \times 10^9/\text{L}$)
- Purulent sputum
- Decline in oxygenation

Data collected will be continuous, nominal, ordinal and discrete.

10.3 Data handling and record keeping

The PI can confirm that patient demographic data electronic data (e.g. Age, DOB, sex, past medical history, head and neck surgical and oncological history) will be transferred from their electronic patient record to the secure networked digital data store. Data will be backed up on a secure trust IT provided memory stick that will be stored in a locked filing cabinet stored within a room that can only be accessed with trust ID. All patient identifiable data and link back spreadsheets will be held at GSTT sites and not transferred to KCL during or after the study.

Any identifiable and personal data will only be accessed by the PI who is an employee of Guy's and St Thomas' NHS Foundation Trust and directly involved in the delivery of clinical care to this patient group, and is held to account on the NHS Trust's information governance policy. All data will be protected and confidentiality maintained following the NHS Code of Confidentiality (2003). Data will only be accessed by the PI and will be stored on a password protected, trust laptop that will be stored in a locked cupboard within an office that can only be accessed with trust ID (rehabilitation room on Blundell ward at Guy's Hospital). The data will be backed up on a trust provided encrypted memory stick.

Any identifiable and personal data will only be accessed by the investigator who is also an employee of Guy's and St Thomas' NHS Foundation Trust and in their clinical role deliver clinical care to this patient group, and is held to account on the NHS Trust's information governance policy. All data will be protected and confidentiality maintained following the NHS Code of Confidentiality (2003).

All data files containing data will be anonymised using a code that does not allow direct identification of the participant. The key to the code will be stored in a separate file together with the personal details of each participants. The key, personal details and log will be stored only on the secure storage facility. This data will be stored using a password-protected excel spreadsheet.

Patient's hospital numbers will not be held in the same database as clinical data. It will be stored in a separate database and linked through a unique study number. On initial identification it will be stored in a separate password protected database that will be saved on a secure trust laptop, stored in a locked cabinet in a room that can only be accessed with trust swipe ID access.

The data (stored on password protected computers that are stored in a secure office of the PI at Guy's Hospital Site) generated by the study will be analysed in commercially available software (SPSS) by the PI.

The data will not include any participant identifiable data. Anonymized participant characteristic and study data for this study will be stored securely in Microsoft Excel files – it is a small non-interventional observational study and while we do not envisage the characteristic data changing, if it does then separate files will be created to create an audit trail.

The data will be analysed on the Guy's Hospital site, on a GSTT laptop, by the PI only. All participant-identifiable data will have already been removed from the laptop and transferred to an encrypted external storage device (an encrypted USB device provided by the GSTT IT department kept in a locked filing cabinet in locked, secured offices in an area that can only be entered with a security swipe-card at Guy's Hospital. The encrypted external storage device will be backed-up on a secure networked digital datastore that is accessible only to the PI on PCs that are password protected at login kept in locked, secured offices in an area that can only be entered with a security swipe-card at Guy's hospital. Any GSTT laptop will not therefore have participant-identifiable data kept on its hard drive.

Excel spreadsheets will be used, data stored within excel spreadsheets will be periodically saved as a PDF (to lock the data) and saved in a password protected folder with the Excel database. The PDF will be printed off and validated by the PI. A hard copy will be retained securely should the Excel file become corrupt as a back-up.

Data Protection:

Data will be processed according to trust information governance processes and the PI is compliant with all information governance mandatory training and good clinical practice principles

No data will be obtained that is not required for the current study and its stated end points

Every effort will be made to ensure data will be recorded accurately and thoroughly checked prior to analysis

Data for the current study will be kept on a secured GSTT trust laptop in a secure, locked office accessed only by trust ID for a maximum of 5 years

All patients identified as eligible for the study will be assigned a code the code will be kept on a secure GSTT trust laptop within a secured locked office at GSTT

No data will be disclosed outside of the EU. The outcomes of the study may presented at national and international conference that may include the EU, and/or published in peer review journals that include the EU - all data will be deidentified.

11 Statistical considerations

Statistician advising on power calculation and analysis procedure.

[name]

Senior Data Manager, NIHR GSTT/KCL Biomedical Research Centre

Visiting Senior Data Manager, School of Population Health & Environmental Sciences, KCL

Guy's & St Thomas' NHS Foundation Trust

[name]

London

[name]

[name]

[contact]

11.1 Sample size calculation (some pilot/feasibility studies may not require a formal sample size calculation)

The sample size required is 193. Using G*Power 3.1.9.2 Universität Düsseldorf: G*Power (hhu.de) the study has been powered at 80%, with a type 1 error of 5%, two-tailed, to detect an effect size difference, expressed as an odds ratio, of 2.33 using binary logistic regression. It is assumed that 30% of patients that did not have a tracheostomy inserted for maxillofacial surgery with free flap reconstruction (2014 cohort) develop HAP. It is further assumed that the 2018 cohort (those with endotracheal intubation) will make up 41% of the combined cohort. The primary independent variable will be binary to represent the two cohorts being studied.

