6.1 Study Design

In 2017, a new maxillofacial surgeon was appointed to Guy's & St Thomas' NHS Foundation Trust who's preference was to insert a temporary tracheostomy for all patients undergoing oromaxillofacial surgery with free flap reconstruction. Prior to this there was a wide variation in case selection with the majority of patients undergoing overnight intubation. Since subsequent practice has now changed and all patients now undergo tracheostomy insertion within OMFS, a prospective design is not possible, therefore, a single site retrospective observational design will be adopted, allowing data from two cohorts of patients identified to be collected within a feasible timeframe dictated by the module deadlines. Electronic and paper notes of patients from cohorts before and after the change in maxillofacial surgical practice (2014 and 2018) will be screened.

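### Does the target of 193 lose its 80% power because the two cohort years are closed, incomplete records are dropped and the 41% cohort is mislabelled?

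*Combined protocol and SAP*

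**What the plan says.** Section 11.1 sets the target: "The sample size required is 193". The synopsis repeats 193 as the number of patients. The inputs are 80% power, two-sided 5%, an odds ratio of 2.33 from logistic regression with cohort as the binary predictor, and a reference rate: "It is assumed that 30% of patients that did not have a tracheostomy inserted" (the 2014 cohort) develop HAP. The allocation is that "the 2018 cohort (those with endotracheal intubation) will make up 41% of the combined cohort".

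Section 7.1 defines the cohorts the other way round from that bracket: "Patients who underwent maxillofacial resection with free flap reconstruction and tracheostomy from 1st January 2018 to 31st December 2018", and intubated patients "with endotracheal intubation from 1st January 2014 to 31st December 2014". The synopsis and Section 6.1 agree with 7.1 on the years. The opening text of Section 7 gives 2017 as the tracheostomy year.

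On supply, Section 7 screens consecutive notes for the named years and adds: "Only those with missing or unavailable data will be excluded". Section 6.1 describes practice before the 2017 appointment: "Prior to this there was a wide variation in case selection with the majority of patients undergoing overnight intubation". Of current practice it says "all patients now undergo tracheostomy insertion within OMFS".

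**The concern.** A retrospective study on two closed years cannot recruit its way out of a shortfall. If 193 is both the number needed and the number to be found, every record excluded as incomplete costs power. The outcome needs a chest x-ray finding plus at least two of four further signs, taken partly from paper notes, so some exclusions are plausible. The plan does not say how many eligible patients each year holds, how many exclusions it expects, or what happens if a cohort is short. The synopsis nevertheless promises adequate power, and Section 11.2 plans a significance test between the cohorts.

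The split adds doubt. Read with 7.1, 2018 supplies 79 tracheostomy patients and 2014 supplies 114 intubated patients. If all patients have a tracheostomy after the change and only a majority were intubated before it, 114 against 79 needs a 2014 caseload at least 114/79 = 1.44 times that of 2018. If the bracket in 11.1 is what was meant, the intubated cohort is the 79. A reader cannot tell which was planned. At stake would be a comparison with less power than stated, and a temptation to widen the years after HAP had been scored.

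**Working it through.** **Inputs.** From 11.1: reference rate p1 = 0.30, OR = 2.33, share B = 0.41, two-sided 5%, power 80%. The documents give no exclusion rate and no caseload; any value used for these below is an assumption.

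**Step 1: the comparison rate.** Odds = 2.33 × 0.30/0.70 = 0.9986, so p2 = 0.9986/1.9986 = 0.4996. The study is powered for 30% versus 50%.

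**Step 2: reproduce 193.** Wald test in logistic regression, with the variance under the null used for the critical value:

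N = (1.960·√V0 + 0.842·√V)² / (ln OR)²

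- V = 1/(0.59 × 0.30 × 0.70) + 1/(0.41 × 0.4996 × 0.5004) = 17.83
- Pooled rate P = 0.59 × 0.30 + 0.41 × 0.4996 = 0.3819
- V0 = 1/(0.3819 × 0.6181 × 0.41 × 0.59) = 17.51
- N = (1.960 × 4.185 + 0.842 × 4.222)² / 0.8459² = 193.2

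The Hsieh formula for a binary covariate gives 191.6. The stated figure stands.

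**Step 3: power at the stated split.** 0.41 × 193 = 79 and 0.59 × 193 = 114. Exact power of the Pearson chi-square test (summing both binomials over tables with a statistic above 3.841) is 80.5%.

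**Step 4: exclusions, under two readings of 193.** If exactly 193 are identified and records are then removed equally from both cohorts:

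| Assumed exclusions | Intubated + tracheostomy | Exact power |
|---|---|---|
| 0% | 114 + 79 | 80.5% |
| 5% | 108 + 75 | 78.2% |
| 10% | 103 + 71 | 76.4% |
| 20% | 91 + 63 | 71.3% |

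If 193 means complete cases, exclusions come off the eligible pool instead. The pool must then be 193/0.90 = 215 or 193/0.80 = 242, and power stays at 80%. The documents do not say whether the pool is below, at or above these numbers.

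**Step 5: the label.** Give the 41% to the intubated cohort, so that the tracheostomy share is 0.59:

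- The Step 2 formula gives 191.0 instead of 193.2, and Hsieh gives 193.8 instead of 191.6. Each moves by about 2.
- The Wald version without the null-variance term moves more, from 195.6 to 201.8, but its power at 193 changes only from 79.5% to 78.2%.
- Exact power at 79 + 114 is 79.6%, against 80.5% at 114 + 79.

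This reading also fits Section 6.1: with equal yearly caseloads, 79/114 = 69% of 2014 patients would have been intubated, which is a majority.

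**Step 6: caseload scenarios.** Suppose both years have 79 patients and between just over half and all of 2014 was intubated. Cohorts of 40 + 79 to 79 + 79 then give 56% to 73% power. Suppose instead both years have 114 patients: 79 + 114 (69% intubated) gives 80%, and 114 + 114 (all intubated) gives 87%. The result is set by the assumed caseload, and no caseload appears in the documents.

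**The case for a change.** The strongest case for acting does not need an assumed rate. The plan claims adequate power from a fixed pool of unstated size, with an exclusion rule and no contingency. The database already exists, so the counts could have been given. The same investigator screens, scores HAP and analyses, so a decision to widen the years should be taken before outcomes are known.

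Most of this is true as description. The eligible count, the exclusion allowance and the shortfall rule are absent, and stating them would have made Section 11.1 clearer. But it does not show that the study misses its stated power. Section 11.1 calls 193 the number required, not the number available. Section 7 takes consecutive eligible cases from the named years and sets no stopping point. The synopsis entry of 193 can be read either way. The plan does not provide for widening the years, so data-driven extension is a risk only if someone departs from it. A number to screen would also do little in a census of closed years, because nobody can be recruited towards it.

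The contradiction in Section 11.1 is real, as is the stray 2017 in Section 7. Neither leaves the cohorts in doubt: the synopsis, 6.1 and 7.1 all use 2014 and 2018, and the synopsis and 7.1 put tracheostomy in 2018.

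The 30% rate has no stated source and lies above the 10% and 6% intubation rates cited in Section 4.5. The protocol itself regards those studies as weak, and the gap alone does not show low power.

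**Conclusion.** The concern does not hold as a reason to change the plan. The target of 193 is correct for its inputs, with exact power of 80.5%. The fall to about 76% or 71% rests on two assumptions that the documents do not support: an exclusion rate of 10% or 20%, and a pool of exactly 193 before exclusions. The lower range of 56% to 73% rests on a yearly caseload of 79 that appears nowhere.

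The wrong airway in the 11.1 bracket and the 2017 in Section 7 are clerical slips to be reconciled with 7.1. The label moves the required N by about 2 and exact power by 0.9 points, so correcting it alters no result.

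The missing count and allowance are a gap that analysts fill in the ordinary course: they analyse every usable 2014 and 2018 case, report the cohort sizes reached, and let the precision of the estimate show what the data support. This conclusion assumes that all eligible cases in both years are taken, as Section 7 says. If the usable total proved well below 193, power would be lower, but the planned comparison would remain valid.
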